Thus, the optimization of training prescription through the manipulation of different training variables, such as weekly frequency, still requires further investigation from a functional, cardiovascular, and metabolic perspective. Therefore, this study aims to investigate the effects of two different weekly frequencies of combined training on functional capacity, blood pressure, and biochemical profile in older adults with cardiometabolic risk factors. We hypothesized that performing three weekly sessions of

combined training would lead to better adaptations in cardiovascular risk factors and functional capacity than performing two weekly sessions.

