2.5. PRIMARY OUTCOME (FUNCTIONAL CAPACITY)

2.5.1. Strength

Lower limb strength was measured using the 30-second sit-to-stand test. The test result used was the number of repetitions performed in this time, in one attempt⁽¹⁴⁾. Upper limb strength was assessed using the 30-second arm curl test, with a 2.0 kg dumbbell for women and a 4.0 kg dumbbell for men. The test result was the total number of curls completed in a single attempt with the dominant arm⁽¹⁴⁾.

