2.5.2. Balance/Agility

Agility/dynamic balance was measured using the Timed Up and Go (TUG) test⁽¹⁵⁾. The test result was the shortest time to stand up from a seated position, walk 3.00 meters, turn around, and return to the seated position. The TUG was performed at two walking speeds (maximum and usual), with two attempts for each, and the shortest time of each speed was recorded.

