2.7. STATISTICAL ANALYSES

The data were analyzed using JASP (Version 0.19.3) [computer software]. The characterization variables had their normality and homogeneity tested using the Shapiro-Wilk and Levene tests, respectively. Variables classified as normal are presented as the mean and standard deviation. Categorical variables for characterizing the sample are presented as absolute frequency (sample n) and relative frequency (%). For comparing baseline characteristics between groups, the independent t -test was used for continuous

data and Fisher's exact test for categorical data. To compare adherence between groups, the Wilcoxon rank sum test was used, and data are presented as median and interquartile range (P25-P75).

For the comparison of the group (G2x and G3x) and time (pre-intervention and post-intervention), a 2-way analysis of covariance (ANCOVA) for repeated measures was performed, with the baseline values used as covariates. Outcomes were analyzed by intention to treat (ITT), which included all patients, once randomized, and missing data were imputed with simple imputation, replacing missing values with the last observed value. The significance adopted was 0.05.

REFERENCES

3. Penninx BWJH, Nicklas BJ, Newman AB, Harris TB, Goodpaster BH, Satterfield S, et al. Metabolic Syndrome and Physical Decline in Older Persons: Results from the Health, Aging and Body Composition Study. *J Gerontol A Biol Sci Med Sci*. 2009 Jan 1;64A(1):96–102.

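### Seven functional tests share one primary outcome at 0.05 with no multiplicity control: if any one counts, a false difference has an 18–30% chance, and one favouring three sessions 9–16% (correlations 0.7 to 0)

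*Combined protocol and SAP*

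**What the plan says.** All references are to the combined protocol and SAP.

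The heading of section 2.5 is singular, "PRIMARY OUTCOME (FUNCTIONAL CAPACITY", but the subsections beneath it yield seven results:

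- 2.5.1: two strength counts. "Lower limb strength was measured using the 30-second sit-to-stand test" and "Upper limb strength was assessed using the 30-second arm curl test".
- 2.5.2: "The TUG was performed at two walking speeds (maximum and usual), with two attempts for each". The best time at each speed is kept, which gives two results.
- 2.5.3: sit-and-reach distance.
- 2.5.4: 6MWT distance and 1000 m time.

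Section 2.6 adds ten secondary outcomes: SBP, DBP, MAP, heart rate, total cholesterol, LDL, HDL, triglycerides, glucose and creatinine.

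Section 2.7 describes a single ANCOVA approach for the outcomes and closes with "The significance adopted was 0.05". The abstract gives the same level. The Introduction's hypothesis is that three weekly sessions of "combined training would lead to better adaptations in cardiovascular risk factors and functional capacity than performing two weekly sessions".

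No section names a lead test, a composite score, an order of testing, an adjustment for multiple tests, or the number of results that must differ before the hypothesis counts as supported.

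**The concern.** A level of 0.05 is the error rate of one test. The trial's claim concerns functional capacity as a whole, and the plan offers seven routes to it without saying how they combine. If one significant result out of seven may be reported as an effect of training frequency on the primary outcome, the error rate of that claim is not 0.05. What is at stake is how a mixed result should be read. With one or two of the seven tests below 0.05, neither the authors nor a reader could tell from the plan whether the hypothesis had been supported.

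**Working it through.** **Inputs**

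- Number of primary results: 7 (sections 2.5.1 to 2.5.4: 2 + 2 + 1 + 2).
- Level: 0.05 (section 2.7). Sidedness is not stated. ANCOVA F tests are non-directional, so two-sided is assumed, with 2.5% of the error in each direction.
- Assumption: one group comparison per measure. The two-way model also yields group, time and interaction tests, and section 2.7 does not say which is decisive.
- Assumption: any one significant measure would be read as support.
- Correlation among the seven: not given. A common value r from 0 to 0.9 is assumed, with every measure oriented so that positive favours three sessions (TUG and 1000 m are times, so lower is better).

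**The plan's own figure.** The plan states only the per-test level. With one test, 1 − 0.95¹ = 0.05, so the stated level is right for one test alone.

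**Independent tests**

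- Either direction: 1 − 0.95⁷ = 1 − 0.6983 = 0.302.
- Favouring three sessions: 1 − 0.975⁷ = 1 − 0.8376 = 0.162.

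**Correlated tests.** Simulation of 1,000,000 draws with no true effect, Zⱼ = √r·C + √(1−r)·Eⱼ for j = 1 to 7, with C and Eⱼ standard normal. A test rejects if |Zⱼ| > 1.96, and favours three sessions if Zⱼ > 1.96.

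| Common r | At least one false positive, either direction | At least one favouring three sessions |
|---|---|---|
| 0 (exact) | 30.2% | 16.2% |
| 0.3 | 27.2% | 13.8% |
| 0.5 | 23.0% | 11.5% |
| 0.7 | 17.8% | 8.9% |
| 0.8 | 14.8% | 7.4% |
| 0.9 | 11.4% | 5.7% |
| Single test | 5% | 2.5% |

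From r = 0 to r = 0.7 the inflation in either direction runs from 30.2/5 = 6.0-fold to 17.8/5 = 3.6-fold. In favour of three sessions it runs from 16.2/2.5 = 6.5-fold to 8.9/2.5 = 3.6-fold.

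A less uniform pattern, with correlation 0.8 within the strength, TUG and aerobic pairs and 0.4 elsewhere, gives 22.5% and 11.3%, close to the r = 0.5 row.

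**With the fix.** Holm's first step is 0.05/7 = 0.00714. If there is no effect on any measure, Holm makes an error only when the smallest p-value passes that step. For independent tests this has probability 1 − (1 − 0.05/7)⁷ = 4.9%. At r = 0.3, 0.5 and 0.7 it is 4.6%, 4.1% and 3.2%.

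**The case against.** Four objections deserve an answer.

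*No success rule is stated, so an any-one rule is the worst case.* This stands as a limit on the size. The hypothesis joins cardiovascular risk factors and functional capacity with an and, and could be read as requiring more than one positive result. If all seven had to favour three sessions, the error would be well under 2.5% (0.7% even at r = 0.9). The documents choose none of these rules, and that gap is itself the defect.

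*The 30% is not the chance of wrongly declaring three sessions better.* Correct. A reader might infer that it is, but it counts errors in both directions and assumes independence. The figure for a false result favouring three sessions is 16% at r = 0 and 9% at r = 0.7, to be set against 2.5%.

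*The tests may be strongly correlated.* At r = 0.9 the directional figure falls to 5.7%, still above 2.5%. A common correlation that high looks unlikely for a set that includes flexibility, arm curls and 1000 m time, but the documents give no value.

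*The problem extends to 17 outcomes.* A reader might infer that any of 17 comparisons could carry the claim, and compute an error rate as if all were independent. The documents do not support this. Section 2.6.1 calculates MAP from SBP and DBP, and section 2.6.2 calculates LDL from total cholesterol, HDL and triglycerides, so 17 independent tests cannot exist. The ten are also already labelled secondary. It remains true that no adjustment or exploratory status is stated for them.

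**Conclusion.** The point holds and should be fixed. The plan does not control the error rate of a claim about its primary outcome, and it does not say what result would support that claim. For assumed correlations between 0 and 0.7, the chance of at least one false difference is several times that of a single test, whether counted in either direction or in favour of three sessions only.

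The sizes rest on four assumptions: two-sided tests, one group comparison per measure, separate testing of each measure, and any one significant result being read as support. Separate testing is inferred, because section 2.7 describes no composite or multivariate test. If more than one model term per measure were used for claims, there would be more tests than counted here.

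The figures cover chance error only. Section 2.3 says the groups could not be randomised, so confounding could produce a false difference whatever the multiplicity procedure. The estimates themselves are unaffected by this point.

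**What to change.** Add to section 2.7:

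> The group comparison for each of the seven primary functional tests is tested with the Holm procedure at family-wise two-sided 0.05; a difference between frequencies is claimed only for tests that pass Holm. Secondary outcomes are exploratory and reported with estimates and 95% CIs, without confirmatory claims. Holm controls chance error only; the groups were not randomised.

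The text should also say which term of the model is the group comparison. Holm is valid under any correlation, so the unknown correlations need not be estimated.

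Naming a single primary test instead is acceptable only if it is chosen before any outcome data are seen. The methods are written in the past tense, so data may already exist. If results are known, apply Holm to all seven and disclose it as post hoc.

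The cost is wording, plus lower power per test: the smallest p-value must be at or below 0.05/7 = 0.0071 before any difference can be claimed. The documents give no sample size or power, so the loss cannot be quantified here.

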APPENDIX B – Anamnesis

I) SOCIODEMOGRAPHIC PROFILE

I.1) Full Name: _____
I.2) Address: _____
I.3) CEP: _____ **I.4) Contact Phone:** _____ **I.5) Mobile:** _____
I.6) In case of emergency, notify (name and phone): _____
I.7) Date of birth: ____/____/____
I.8) Marital status: (0) Married/partnered (2) Single
(1) Separated/divorced (3) Widowed
I.9) Education level: (0) Incomplete elementary school (1) Incomplete high school
(2) Elementary school completed (3) High school completed (4) Incomplete higher education
(5) Higher education completed

II) HEALTH HISTORY

II.1) Has a doctor ever told you that you have or have had:

II.1.1) Coronary artery disease (0) No (1) Yes How long? _____
II.1.2) Hypertension / high blood pressure (0) No (1) Yes How long? _____
II.1.3) Diabetes (high blood sugar) (0) No (1) Yes How long? _____
II.1.4) High cholesterol and/or triglycerides (blood fat) (0) No (1) Yes How long? _____
II.1.5) Pulmonary disease (asthma, emphysema, COPD, etc.) (0) No (1) Yes How long? _____
II.1.6) Enlarged heart or history of heart transplant (0) No (1) Yes How long? _____
II.1.7) Arrhythmias, dysrhythmias, or heart failure (0) No (1) Yes How long? _____
II.1.8) Aneurysm, stroke, or cerebrovascular accident (0) No (1) Yes How long? _____
II.1.9) Heart valve disease (0) No (1) Yes How long? _____
II.1.10) Chagas disease (0) No (1) Yes How long? _____
II.1.11) Blocked artery, myocardial infarction (heart attack), or coronary bypass surgery (0) No (1) Yes
How long? _____
II.1.12) Other diseases or health problems? _____

II.1.13) Are you under medical supervision? (0) No (1) Yes

II.2) Do you feel chest pain (angina)? If yes, how often?

II.3) Which medications do you regularly use (Include name, dose, weekly frequency, and time of day)?

II.4) Do you have any physical limitation (pain, injury, or surgery involving bones, muscles, or joints) that limits or prevents physical activity?

II.5) During physical activity have you ever experienced any of these symptoms?

1. Chest pain or discomfort (0) No (1) Yes
2. Shortness of breath during light exercise (0) No (Yes)
3. Dizziness or fainting (0) No (1) Yes
4. Palpitations or tachycardia (0) No (1) Yes
5. Leg pain when walking (0) No (1) Yes
6. Severe fatigue during light activities (0) No (1) Yes

II.6) Has any first-degree relative had heart disease? (0) No (1) Yes (7) Don't know
II.7) Do you currently smoke? (0) No (1) Yes
II.7.1) If yes, on average how many cigarettes do you smoke per day? ____ cigarettes (7) Don't know (8) Not applicable
II.8) Have you had COVID-19? (0) No (1) Yes

V. QUALITY OF LIFE ASPECTS

Please answer all questions. If you are unsure about how to respond, choose the option that seems most appropriate. This is often your first choice. Please consider your values, aspirations, pleasures, and concerns. We are asking about your perception of your life over the **LAST TWO WEEKS**.

V.1) How would you rate your quality of life?

() Very poor () Poor () Neither poor nor good () Good () Very good

V.2) How satisfied are you with your health?

() Very dissatisfied () Dissatisfied () Neither satisfied nor dissatisfied () Satisfied () Very satisfied

V.3) How satisfied are you with your ability to perform daily activities?

() Very dissatisfied () Dissatisfied () Neither satisfied nor dissatisfied () Satisfied () Very satisfied

V.4) How satisfied are you with yourself?

() Very dissatisfied () Dissatisfied () Neither satisfied nor dissatisfied () Satisfied () Very satisfied

V.5) How satisfied are you with your personal relationships? (friends, relatives, acquaintances)

() Very dissatisfied () Dissatisfied () Neither satisfied nor dissatisfied () Satisfied () Very satisfied

V.6) How satisfied are you with your living conditions?

() Very dissatisfied () Dissatisfied () Neither satisfied nor dissatisfied () Satisfied () Very satisfied

V.7) Do you have enough energy for your daily life?

() None () Very little () Moderate () A lot () Extremely

V.8) Do you have enough money to meet your needs?

() None () Very little () Moderate () A lot () Extremely
